3. OBJECTIVES AND ENDPOINTS

| Objectives | Endpoints |
|--|--|
| Primary | |
| To compare the clinical effect of a single intravenous (IV) infusion of 2 mg/kg of GSK1070806 versus placebo in moderate to severe Atopic Dermatitis in the Biologic Naïve (BN) population (Group 1). | Percent change from baseline (PCFB) in the Eczema Area and Severity Index (EASI) at Week 12 (Section 8.1.1). |
| Secondary | |
| To further compare the clinical effect (GSK1070806 versus placebo) in the BN population (Group 1). | Change from Baseline (CFB) in the EASI at Week 12. EASI 50/75/90 defined as ≥ 50/75/90% reduction in the EASI from Baseline at Week 12. Investigator Global Assessment (IGA) score of 0 or 1 at Week 12. |
| To estimate the clinical effect of GSK1070806 in the dupilumab inadequate responder (Dupi-IR) population (Group 2). | PCFB in the EASI at Week 12. |
| To assess safety and tolerability (GSK1070806 versus placebo) in the combined AtD population (Groups 1 and 2). | Incidence of serious adverse events (SAEs) and adverse events (AEs). Incidence of clinically important (1) findings in: |

| Objectives | Endpoints |
|---------------------------------|---|
| | vital signs |
| | electrocardiogram |
| | laboratory: haematology, clinical |
| | chemistry and urinalysis. (Section 8.3) |
| To assess anti-drug antibody | Incidence of ADAs (Section 8.8) |
| (ADA) formation in the combined | |
| AtD population (Groups 1 and 2) | |

| Objectives | Endpoints |
|------------|-----------|

1) Absolute or change in important clinical findings are defined in the statistical analysis plan (SAP) for each relevant safety endpoint.

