10.2. Appendix 2: Clinical Laboratory Tests

The tests detailed in Table 1 will be performed by the central laboratory.

Local laboratory results are only required in the event that the central laboratory results are not available in time for either study intervention administration and/or response evaluation. If a local sample is required, it is important that the sample for central analysis is obtained at the same time. Additionally, if the local laboratory results are used to make either a study intervention decision or response evaluation, the results must be recorded.

Protocol-specific requirements for inclusion or exclusion of participants are detailed in Section 5 of the protocol.

Additional tests may be performed at any time during the study as determined necessary by the investigator or required by local regulations.

Table 1 Protocol-Required Safety Laboratory Tests

| Laboratory Assessments | Parameters | | | | | |
|------------------------------------|--|---------------------------|---|--|---|----------------------------|
| Hematology | Platelet Count Red Blood Cell (R Count Hemoglobin Hematocrit | BC) | RBC Indices: Mean Corpuscular Volume (MCV) Mean Corpuscular Hemoglobin (MCH) %Reticulocytes Absolute reticulocyte count | | White Blood Cell (WBC) count with Differential: Neutrophils Lymphocytes Monocytes Eosinophils Basophils | |
| Clinical Chemistry ¹ | Blood Urea Nitrogen (BUN) | Potassium | | Aspartate Aminotransferase (AST)/ Serum Glutamic- Oxaloacetic Transaminase (SGOT) | | Total and direct bilirubin |
| | Creatinine | Sodium Corrected calcium | | Alanine Aminotransferase (ALT)/ Serum Glutamic-Pyruvic Transaminase (SGPT) Alkaline phosphatase ² | | Total Protein and albumin. |

| Laboratory Assessments | Parameters |
|---------------------------|--|
| Routine Urinalysis | Specific gravity pH, glucose, protein, blood, ketones, bilirubin, nitrite, leukocyte esterase, by dipstick Microscopic examination (if blood or protein is abnormal) |
| Pregnancy testing | Highly sensitive serum or urine human chorionic gonadotropin (hCG) pregnancy test (as needed for women of childbearing potential)3 |
| Other Screening | Follicle stimulating hormone (FSH) and estradiol (as needed in women of non-childbearing potential only) |
| Tests | Alcohol and urine drug screen (to include at minimum: amphetamines, barbiturates, cocaine, opiates, cannabinoids and benzodiazepines)] |

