4.5.3.2. Vital Signs

A summary table of change from baseline in vital signs will be produced, including systolic blood pressure (SBP), diastolic blood pressure (DBP), heart rate, and temperature.

Shift tables of worst-case results relative to PCI criteria post-baseline relative to baseline will be provided for SBP, DBP and heart rate (see Section 6.2.1).

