4.5.3.3. ECG

For all ECG analyses, baseline is taken to be the mean of the triplicate values collected pre-dose Day 1. The following summaries will be provided:

- 1. Summary of Maximum QTc Values Post-Baseline Relative to Baseline by Category
- 2. Summary of Maximum Increase in QTc Values Post-Baseline Relative to Baseline by Category
- 3. Summary of ECG findings (the clinical significance and interpretation of each planned ECG). In the case of triplicate ECG measurements, results will be presented separately by measurement number.
- 4. Summary of change from baseline in ECG values. In the case of triplicate ECG measurements, summaries will use the average of the triplicate.

The QTc data analysis will use the values based on Fridericia formula. For analysis purposes, if QTcF is not available, it will be derived from QTcB.

Shift tables will be provided for QTcF and will be used to detect any clinically important changes:

- Maximum QTc values post-baseline relative to baseline by category defined as
 - o To ≤450msec or No Change
 - o Any increase > 450 msec

- \circ Increase to >450 to <=480
- \circ Increase to >480 to <=500
- o Increase to >500 msec
- Maximum increase in QTc values post-baseline relative to baseline by category defined as:
 - Increase of \leq 30 msec
 - o Increase between 31 and 60 msec
 - o Increase > 60 msec

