6.2. Appendix 2 Data Derivations Rule

6.2.1. Criteria for Potential Clinical Importance

6.2.1.1. Laboratory Values

Haematology					
Laboratory Parameter	Units	Category	Potential Clinical Importance		
			Low Flag (< x)	High Flag (>x)	
		Male	<0.1	>0.54	
Hematocrit	Ratio of	Female	<0.1	>0.54	
Hematocht	1	Δ from BL	>0.075 change from baseline		
	g/L	Male	<100	>185	
Haemoglobin		Female	<100	>165	
Tidemoglobiii		Δ from BL	>25 change from baseline		
Lymphocytes	x10 ⁹ / L		0.8		
Neutrophil Count	x10 ⁹ / L		1.5		
Platelet Count	x10 ⁹ / L		<100	>999	
While Blood Cell Count (WBC)	x10 ⁹ / L		<2		

Clinical Chemistry		
Laboratory Parameter	Units	Potential Clinical Importance
		Low Flag (< x) High Flag (>x)
Albumin	g/L	<30
Corrected Calcium	µmol/L	
-Ages 18-59 years		<1.5 >3.25
-Ages 60-90 years		<1.5 >3.25
Creatinine	µmol/L	
-Male ≥18 yrs	μmol/L	Change from baseline >44.2
-Female ≥18 yrs	µmol/L	Change from baseline >44.2

Clinical Chemistry					
Laboratory Parameter	Units	Potential Clinica	Potential Clinical Importance		
		Low Flag (< x)	High Flag (>x)		
Potassium	mmol/L	<3.0	>6.5		
Sodium	mmol/L	<130	>160		
Blood Urea Nitrogen (BUN)	mg/dl		>40		

Liver Function			
Laboratory Parameter	Units	Category	Potential Clinical Importance
ALT/SGPT	U/L	High	≥ 3x ULN
AST/SGOT	U/L	High	≥ 3x ULN
Alkaline Phosphatase	U/L	High	≥ 2x ULN
Total Bilirubin	µmol/L	High	≥ 2x ULN
Direct Bilirubin			>35%

Urinalysis

A participant is considered to have urinalysis results of PCI, if there is an increase in Protein or an increase in Occult Blood results during the study, or if microscopy is performed.

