6.2.5. Multiple measurements at One Analysis Time Point

When triplicate ECG assessments are taken, mean of the measurement will be calculated first and summary statistics will be based on the calculated mean. This will apply to both screening, baseline, and post baseline assessments.

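### The SAP's urinalysis rule counts any microscopy as a clinically important finding, and its temperature, PR and QRS limits feed no listed table

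*SAP*

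**What the plan says.** Protocol section 3 makes the incidence of clinically important findings in vital signs, ECG and laboratory tests (urinalysis included) a secondary endpoint for Groups 1 and 2 combined. Its footnote passes the definition on: "Absolute or change in important clinical findings are defined in the statistical analysis plan (SAP) for each relevant safety endpoint". The criteria are those for potential clinical importance (PCI) in SAP section 6.2.1.

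- **Urinalysis.** Under SAP 6.2.1.1 a participant has a PCI result "if there is an increase in Protein or an increase in Occult Blood results during the study, or if microscopy is performed". Protocol section 10.2, Table 1, sets the trigger for that test: "Microscopic examination (if blood or protein is abnormal".
- **Vital signs.** SAP 6.2.1.3 sets absolute limits for systolic and diastolic pressure, heart rate and temperature (≤35.5 and >38.0 °C). SAP 4.5.3.2 then plans the following: "Shift tables of worst-case results relative to PCI criteria post-baseline relative to baseline will be provided for SBP, DBP and heart rate".
- **ECG.** SAP 6.2.1.2 sets limits for QTcF, PR (<110, >220 msec) and QRS (<75, >110 msec). The category tables in SAP 4.5.3.3 are for QTc: "Shift tables will be provided for QTcF and will be used to detect any clinically important changes". The middle category of increase there is "Increase between 31 and 60 msec", whereas 6.2.1.2 uses >30 to ≤60 msec. Triplicates are averaged under SAP 6.2.5: "When triplicate ECG assessments are taken, mean of the measurement will be calculated first".
- **Calcium.** The row "Corrected Calcium" in SAP 6.2.1.1 gives limits of <1.5 and >3.25 for both age bands, in µmol/L.

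**The concern.** The endpoint counts participants who meet a rule, so the wording of the rule settles the result. A rule met because a test was run, whatever the test showed, counts participants in whom nothing changed. A limit with no table leaves participants who crossed it uncounted.

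The numbers are small enough for single participants to show. The plan has 20 + 15 = 35 participants on active treatment and 10 + 3 = 13 on placebo. One wrongly flagged participant moves the placebo incidence by 1/13 = 7.7 percentage points and the active incidence by 1/35 = 2.9 points. Among the parameters without a table, temperature matters most, because susceptibility to infection is the first risk listed in protocol section 2.3.1.

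**Working it through.** The plan states no figure for this endpoint, so there is nothing to reproduce. The rules were checked against each other.

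1. **Urinalysis logic.** Abnormal dipstick blood or protein leads to microscopy (protocol 10.2), and microscopy leads to PCI (SAP 6.2.1.1). Neither step asks for a change from baseline or for an abnormal microscopy result. Three kinds of participant therefore meet the definition with no worsening: those with an unchanged baseline abnormality, those whose abnormality is improving but still present, and those whose microscopy is normal.

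2. **Urinalysis size.** The expected number flagged without an increase is N × p. N = 48 (SAP section 5), and p is the proportion with a stable abnormal dipstick, which the documents do not give. Assumed range:
   - p = 5%: 48 × 0.05 = 2.4
   - p = 10%: 48 × 0.10 = 4.8
   - p = 20%: 48 × 0.20 = 9.6

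   Without the microscopy clause these participants are not flagged.

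3. **Limits matched to displays.** Seven vital-sign and ECG parameters have PCI limits. Systolic pressure, diastolic pressure and heart rate have PCI shift tables (SAP 4.5.3.2). QTc has category tables (SAP 4.5.3.3). Temperature, PR and QRS have neither, so 3 of 7 have no planned incidence of crossing the limits.

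4. **Calcium unit.** The documents give no reference range. Assuming normal corrected calcium of 2.1 to 2.6 mmol/L, multiplying by 1,000 gives 2,100 to 2,600 µmol/L. All of these exceed 3.25, so every normal value would be high in the printed unit. In mmol/L, 2.1 to 2.6 lies inside 1.5 to 3.25 and none is flagged. The numbers fit only mmol/L, which the same table uses for potassium and sodium.

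5. **QTc categories.** SAP 4.5.3.3 takes the pre-dose triplicate mean as baseline. If readings are whole milliseconds (an assumption), changes can fall on thirds. On that grid, 30.33 and 30.67 msec belong to none of ≤30, 31 to 60 and >60. Under the PCI table in 6.2.1.2 both fall in >30 to ≤60, and no value is left out. To size this, a simulation with no drug effect took the largest increase over two post-dose triplicate means and two later single readings. Each triplicate reading had SD s/√2 about the participant's own level, and the later single readings 1.5 times that. The share of participants in the gap was:
   - s = 8 msec: 0.02%, or 0.01 of 48
   - s = 12 msec: 0.30%, or 0.14 of 48
   - s = 16 msec: 0.68%, or 0.33 of 48

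**The case against.** The strongest reply is that little of this reaches a planned table. SAP 4.5.3.1 plans worst-case shift tables relative to baseline, with categorical urinalysis parameters listed separately, and there a stable abnormality shows as unchanged. The SAP names no table that counts microscopy as an event, and a screen for potential importance may reasonably be sensitive. This stands in part: the shift tables soften the effect and no inflated output can be pointed to. They do not repair the definition, which is the SAP's only stated criterion for a urinalysis finding.

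On temperature, a reader might infer that fever goes unreported. The documents do not support that. Temperature is in the change-from-baseline table (SAP 4.5.3.2). Vital-sign results that the investigator judges clinically significant are adverse events (protocol 10.3.1) and are tabulated as such (SAP 4.5.2). ECG values and the clinical significance of each planned ECG are also summarised (SAP 4.5.3.3). What remains is narrower: none of these displays gives the incidence of crossing the SAP's own limits. The Output and Programming Specification, which is not public, may add displays.

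On calcium, a reader might infer that every participant will be flagged. That happens only if results are converted to the printed unit before comparison. Baselines would then be flagged too, so a shift table would show no change and the slip would be noticed. On QTc, a reader might infer that the PCI rule has a gap. It does not; only the display categories in 4.5.3.3 do, and rounding, which nothing forbids, would close it.

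**Conclusion.** The concern holds in a limited form. The urinalysis definition is wrong as written because it measures whether a test was run and not whether a finding arose. Its size is unknown from the documents; about 2 to 10 of 48 rests wholly on the assumed 5% to 20% rate of stable abnormal dipsticks. The missing incidence for temperature, PR and QRS is a real but modest omission, judged on the displays the SAP itself lists. The calcium label and the QTc categories are minor corrections: the first rests on an assumed normal range, and the second is expected to affect well under one participant. Only secondary safety reporting is touched. The primary analysis and the operating characteristics are unaffected.

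**What to change.** - **Urinalysis (SAP 6.2.1.1):** delete the microscopy clause, or replace it with a condition that microscopy shows a new or worse abnormality than at baseline.
- **Displays (SAP 4.5.3.2 and 4.5.3.3):** add temperature, and also PR and QRS, to the worst-case PCI shift tables, using the limits already in 6.2.1.
- **Calcium (SAP 6.2.1.1):** confirm the unit against the laboratory data and correct the label to mmol/L.
- **QTc (SAP 4.5.3.3):** use the same increase cut as 6.2.1.2, so that the two sections agree and every value has a category.

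The cost is a few lines of SAP text and a few extra table rows on data already collected. The changes are best made before unblinding.

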6.2.1.2. ECG

ECG Parameter	Units	Potential Clinical Importance		
		Lower Limit	Upper Limit	
Absolute				
		> 450	≤ 480	
Absolute QTc(F) Interval	msec	> 480	≤ 500	
		> 500		
Absolute PR Interval	msec	< 110	> 220	
Absolute QRS Interval	msec	< 75	> 110	
Change from Baseline				
Increase from Pagaline OTo(E)		> 30	≤ 60	
Increase from Baseline QTc(F)	msec	> 60		

6.2.1.3. Vital Signs

Vital Sign Parameter Units		Potential Clinical Importance		
(Absolute)		Low Flag	High Flag	
Systolic Blood Pressure	mmHg	< 85	> 160	
Diastolic Blood Pressure	mmHg	< 45	> 100	
Heart Rate	bpm	< 40	> 110	
Temperature	°C	≤ 35.5	> 38.0	

Vital Sign Parameter	Units	Potential Clinical Importance			
(Change from Baseline)		Decrease from	Decrease from Baseline Increase from		
		Lower Limit	Upper Limit	Lower Limit	Upper Limit
Systolia Pland Prossura	mm∐a	≥ 20	< 40	≥ 20	< 40
Systolic Blood Pressure	mmHg	≥ 40		≥ 40	
Digetalia Bland Brassura	mm∐a	≥ 10	< 20	≥ 10	< 20
Diastolic Blood Pressure	mmHg	≥ 20		≥ 20	
Heart Data	ham	≥ 15	< 30	≥ 15	< 30
Heart Rate	bpm	≥ 30		≥ 30	

Note: For a Parameter, separate rows denote categories of PCI. For example, for Systolic Blood Pressure, an Increase from Baseline of >= 20 mmHg to < 40 mmHg falls into a lower increase PCI category, and an Increase from Baseline of >=40 mmHg falls into a higher increase PCI category.

6.2.2. Study Period

Assessments and events will be classified according to the time of occurrence relative to the study intervention period.

Pre-Intervention is defined as time prior to the first dose of study intervention.

Treatment period is defined as time from first dose to and including Week 12 visit. If time of assessment or study intervention is not collected, the following assessment on the first dose date will be assumed to be taken prior to the first dose and therefore considered pre-intervention: ECG, Lab, and vital signs, and first dose date is considered on-intervention for AE and concomitant medication.

Follow up is defined as any time post on-intervention window, i.e. \geq Week 12 visit + 1 day.

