- Group 1: Patients naïve to biologic treatment (and who have failed topical therapies).
- Group 2: Patients who have not adequately responded (or have been intolerant) to dupilumab (Dupixent).

All participants must wash out topical therapies (corticosteroids, calcineurin inhibitors, phosphodiesterase (PDEIV) inhibitors) for at least 7 days prior to dosing on Day 1.

All participants are required to undergo Coronavirus strain 19 (COVID-19) testing prior to dosing and at the End of Study.

Changes in the clinical signs of AtD as well as changes in disease biomarkers in blood and in skin (*via* serial biopsies and tape stripping) are to be assessed as well as patient reported outcomes (itch, sleep disturbance, fatigue), pharmacokinetics and anti-drug antibodies.

The primary completion is at Week (Wk) 12 and the End of Study Visit is at Wk 24.

Nine outpatient visits are scheduled: Screening (1), Treatment Period (6), Follow-Up Period (2). Skin biopsies and tape strips will be collected on Day 1 (prior to dosing), Wks 4 and 12.

Number of Participants:

Approximately 64 patients are expected to be screened to achieve approximately 48 randomly assigned participants.

Intervention Groups and Duration:

[figure not shown]
A single 2 mg/kg one-hour IV infusion of either GSK1070806 or placebo is to be administered as follows:

- Group 1: N = 30. 20 participants will receive GSK1070806, 10 will receive placebo.
- Group 2: N = 18. 15 participants will receive GSK1070806, 3 will receive placebo.

The study duration for an individual participant is not expected to exceed 28 weeks (Screening 4 is weeks; Treatment Period is 12 weeks; Follow-Up Period is 12 weeks).

Data Monitoring/ Other Committee: An internal safety review team will review blinded safety data. A data review committee may conduct an interim analysis(es) on unblinded data.

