1.3.2. Treatment / Follow-Up Period

| PROCEDURE | TREATMENT Period | | Follow-Up | | | NOTES: a) Primary Endpoint = Day 85 (Wk 12). b) End of Study = Day 169 (Wk 24) | | | | | | |
|--|--|-------|-----------|-------|------|--|--------------------------------|---|-----------------|--------|---|--|
| End of V | VEEK | 1 | 2 | 4 | 8 | ^a 12 | 16 | ^b 24 | Unsch eduled | | Visit Windows: Days 8 to 29 (±1), Days 57 to 113 (±2), Day 169 (±3). | |
| DAY | 1 | 8 | 15 | 29 | 57 | 85 | 113 | 169 | Visit | aw | Visit Villadius: 54/5 5 to 25 (21), 54/5 57 to 115 (22), 54/ 105 (25). | |
| Discharge from clinical unit | X | | | | | | | | | | Discharge not sooner than 2 hours post- end of infusion. | |
| Inclusion/Exclusion Criteria | Χ¹ | | | | | | | | | | 1) Re-check clinical status before dosing on Day 1. | |
| Alcohol Screen | Х | | | | | | | | | | Method per standard local practice (e.g. urine alcohol due to COVID) | |
| Physical Examination (Full ¹ / Brief) | (X) 1 | Х | Х | Х | Х | Х | Х | Χ¹ | X | Χ¹ | 1) Full. | |
| 12-lead ECG | (X) 1 | | | | | Х | | Х | Х | Х | 1) Triplicate Readings. On Day 1: pre-dose, then 30 and 60 mins post-start of infusion. | |
| Vital Signs | (X) 1 | Х | Х | Х | х | Х | Х | X | Х | Х | 1) Dosing Day 1: pre-dose, 30 mins, 1, 1.5 and 2 hrs post-end of infusion. | |
| Pregnancy Test | (X) | | | x | х | х | х | х | | х | High sensitivity urine pregnancy test (or serum testing if required by local regulations) | |
| Haematology, Clinical Chemistry | (X) | Х | Х | Х | Х | Х | Х | Χ | Х | Х | See Appendix 2. | |
| Jrinalysis | (X) | | | Х | | Х | | X | X | Х | See Appendix 2. | |
| COVID-19 (SARS-CoV-2) | (X ¹) | < | | | X² | | > | х | X ³ | x | NEGATIVE RESULT must be obtained prior to dosing. 2) Ad hoc test in case of symptoms. 3) If necessary (at investigator's discretion). | |
| EASI | (X) | | X | X | X | Х | X | X | X | Х | | |
| GA | (X) | | X | X | X | X | Χ | X | X | X | | |
| PP-NRS (itch) | <daily< td="">	>	X	X	Weekly: end of Wks 1, 2, 3, 4.	</daily<> | | | > | X | X | Weekly: end of Wks 1, 2, 3, 4. | | | | | |
| -Sleep Disturbance 8b | (X) | ٧ | /eek | dy | | Bi- | weekl | у | X | Х | Bi-Weekly: every two weeks, starting at the end of Wk 6. | |
| FACIT-Fatigue (13 items) | (X) | ٧ | /eek | dy | | Bi- | weekl | у | Х | X | | |
| CCI | < | | | -Dail | y | | > | | X | Х | | |
| DLQI: Dermatology Life Quality Index | (X) | ٧ | /eek | dy | | Bi- | weekl | у | X | Х | | |

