9.4.1.2. Baseline definition

The baseline value will be the latest pre-dose assessment with a non-missing value, including those from unscheduled visits. If time is not collected, Day 1 assessments are assumed to be taken prior to first dose and used as baseline.

If baseline data is missing, no derivation will be performed, and baseline will be set to missing.

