4.1.2. Baseline Definition

For all endpoints the baseline value will be the latest pre-dose assessment with a non-missing value, including those from unscheduled visits, unless otherwise stated. If time is

not collected, Day 1 assessments are assumed to be taken prior to first dose and used as baseline.

If baseline data is missing no derivation will be performed and baseline will be set to missing.

For PP-NRS and Item 3 baseline, the baseline score will be averaged from daily values from Day -7 to Day -1, if ≥ 4 (out of 7) days are not missing. If only ≤ 3 days (out of 7) are available, baseline is set to missing.

For skin punch biopsy, there is a Lesional Baseline and a Non-lesional Baseline.

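### When times are not collected, the SAP treats all Day 1 vital signs and ECGs as pre-dose, although most are scheduled after the infusion starts

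*SAP*

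**What the plan says.** SAP 6.2.2 (Study Period) has a fallback for when the time of assessment or of study intervention is not collected. For ECG, laboratory and vital-sign data, "the following assessment on the first dose date will be assumed to be taken prior to the first dose", which places them in the pre-intervention period. The same sentence puts adverse events and concomitant medication on the first dose date in the on-intervention period.

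SAP 4.1.2 gives the general baseline rule, which applies unless another is stated: "For all endpoints the baseline value will be the latest pre-dose assessment with a non-missing value". Protocol 9.4.1.2 adds: "If time is not collected, Day 1 assessments are assumed to be taken prior to first dose and used as baseline". SAP 4.1.2 repeats this almost word for word ("Day 1 assessments are assumed to be taken prior to first dose and used as" baseline).

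The Schedule of Activities (Protocol 1.3.2) has repeated Day 1 readings. For vital signs: "Dosing Day 1: pre-dose, 30 mins, 1, 1.5 and 2 hrs post-end of infusion". For the triplicate ECG: "On Day 1: pre-dose, then 30 and 60 mins post-start of infusion". The infusion lasts one hour (Protocol 1.1: "A single 2 mg/kg one-hour IV infusion of either GSK1070806 or placebo").

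SAP 4.5.3.2 reports worst-case post-baseline shifts in blood pressure and heart rate. SAP 4.5.3.3 reports maximum post-baseline QTc and maximum QTc increase. SAP 4.5.3.3 also sets its own ECG baseline, the mean of the pre-dose Day 1 triplicate. Vital signs have no such sentence.

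**The concern.** A pre-dose assumption suits an assessment made once, before dosing. Day 1 safety laboratory samples are of that kind, because the Schedule of Activities has Day 1 blood samples taken before dosing unless it says otherwise. Day 1 vital signs and ECGs are not: most are scheduled specifically to follow the start of infusion.

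These are the only scheduled readings that can show an acute effect of the infusion. The next vital signs are at Day 8 and the next ECG at Day 85. Clinically important vital-sign and ECG findings are a secondary endpoint. Protocol 2.3.1 lists both infusion-related effects and blood pressure as potential risks. On blood pressure it cites hypertension in 2 of 13 and 3 of 12 diabetic participants on two active dose levels and none on placebo, while noting that a detailed review suggested no overall trend. A rule that moves infusion-day readings into the pre-treatment period works against the purpose of taking them.

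**Working it through.** There is no plan figure to reproduce. The check counts scheduled readings and follows them through the rules.

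**Step 1. Day 1 readings for which the assumption is false (Protocol 1.3.2)**

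| | Pre-dose | After infusion start | Share after start |
|---|---|---|---|
| Vital-sign sets | 1 | 4 | 4/5 = 80% |
| ECG triplicates | 1 | 2 | 2/3 = 67% |
| Together | 2 | 6 | 6/8 = 75% |

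The infusion lasts 60 minutes, so the two later ECGs fall during it and at its end.

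**Step 2. Loss from the post-baseline data if the rule covers a participant's whole Day 1**

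This takes a reading classed as pre-intervention to be excluded from post-baseline summaries, which is the natural reading of the SAP.

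- Vital signs: 4 on Day 1 plus Days 8, 15, 29, 57, 85, 113 and 169 make 4 + 7 = 11 scheduled post-baseline sets. Lost: 4/11 = 36%.
- ECG: 2 on Day 1 plus Days 85 and 169 make 2 + 2 = 4. Lost: 2/4 = 50%.
- Upper bound over 48 participants: 48 × 4 = 192 vital-sign sets and 48 × 2 = 96 ECG triplicates. The lower bound is zero.

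**Step 3. Which value becomes the vital-sign baseline**

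- *Assessment times present, dose time absent.* All five Day 1 sets are assumed pre-dose. The latest is the 2-hour post-infusion set, and it becomes baseline.
- *Some or all assessment times absent.* The untimed sets are assumed pre-dose, but which set is latest cannot be settled by clock time. SAP 6.2.5 deals only with ECG triplicates and gives no tie rule. A post-infusion set could be used, but the SAP does not dictate it.

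For ECG the question does not arise in the same way, because SAP 4.5.3.3 is one of the exceptions for which SAP 4.1.2 makes room. What is left for ECG is the Step 2 loss.

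**Step 4. Direction of a displaced vital-sign baseline**

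Assumed systolic values, judged against the 20 mmHg change categories in SAP 6.2.1.3:

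- 130 pre-dose, 155 at 2 hours, 150 at Week 4. Correct changes are 155 − 130 = +25 and 150 − 130 = +20, both flagged. With 155 as baseline, the Day 1 rise disappears and Week 4 is 150 − 155 = −5, not flagged.
- 130 pre-dose, 155 at 2 hours, 130 at Week 4. The correct Week 4 change is 0. With 155 as baseline it is 130 − 155 = −25, a spurious flagged fall.
- 130 pre-dose, 105 at 2 hours, 130 at Week 4. The correct Week 4 change is 0. With 105 as baseline it is 130 − 105 = +25, a spurious flagged rise.

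The loss of the acute reading always conceals it. The effect on later changes can go either way.

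**Step 5. Consistency within SAP 6.2.2**

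Under the one sentence, an untimed Day 1 hypertension event counts as on-intervention, while the untimed blood-pressure reading behind it counts as pre-intervention.

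**The case against.** The strongest reply is that the rule may never operate. It applies when time is not collected, which can be read as a matter of case report form design rather than of occasional gaps. Protocol 6.4 requires the date and time of each dose in the source documents, and nothing says that vital-sign or ECG times go unrecorded. This stands as a limit on frequency. It does not make the rule right when it is used, and there is no matching statement that vital-sign and ECG clock times are recorded.

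Acute safety is also captured elsewhere. Day 1 adverse events count as on-intervention, clinically significant abnormal readings are to be reported as adverse events, participants are observed for at least two hours after the infusion, and the safety review team sees vital signs. This limits the harm, but the vital-sign and QTc summaries would still be wrong for the participants affected.

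A reader might infer four stronger things that the documents do not support:

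- *That the ECG baseline is displaced too.* SAP 4.5.3.3 fixes it as the pre-dose triplicate.
- *That the 2-hour vital-sign set always becomes baseline.* That follows clearly only when assessment times exist and the dose time does not, and the dose time is the item Protocol 6.4 requires.
- *That every distortion hides harm.* Step 4 shows spurious flags as well as lost ones.
- *That all 48 participants are affected.* That is an upper bound which depends on a case report form the documents do not show.

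**Conclusion.** The fallback contradicts the study's own schedule and gives the wrong period for 4 of 5 Day 1 vital-sign sets and 2 of 3 Day 1 ECG triplicates whenever it is triggered. No other section corrects this by planned time point. The consequence for both measures is that infusion-day readings drop out of the worst-case post-baseline summaries. For vital signs alone there is a further risk that a post-infusion value serves as baseline, with bias in either direction.

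The size in practice depends on how often a time is not collected. The documents do not say, so it ranges from no participants to all 48 and may well be low. The endpoint is secondary and descriptive, with no formal testing of safety data. The primary EASI analysis is not affected. This is a modest defect, but a definite one, and worth correcting before unblinding.

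**What to change.** 1. In SAP 6.2.2 and 4.1.2, state that where time is not available, the planned (nominal) time point decides whether a Day 1 vital sign or ECG is pre-dose or post-dose.
2. In SAP 4.5.3.2, or as a stated exception in 4.1.2, add a vital-sign baseline sentence matching the ECG one: baseline is the nominal pre-dose Day 1 assessment.
3. Keep the pre-dose assumption only for assessments scheduled solely before dosing on Day 1, such as the safety laboratory tests.
4. Align Protocol 9.4.1.2, which carries the same baseline assumption, or record the change in SAP 4.8, which at present declares no departure from the protocol analyses.

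With the planned time point in use, all 4 post-infusion vital-sign sets and both later ECG triplicates count as post-baseline even if untimed, and only the nominal pre-dose reading is baseline. The cost is a few sentences in the SAP plus a protocol alignment or an entry in SAP 4.8. No new data are needed, because the planned time points are already in the Schedule of Activities; this assumes that each Day 1 record carries its time-point label.
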